13.1. Blinding

The randomised treatment allocation will not be blinded to physician or patient, but participating

centres will only be unblinded to treatments given in their own site. Summary details of randomised

allocation and outcomes will not be made available (unless specifically authorised by the TSC and/or

DMC), in order to maintain the overall blind of the trial.

The statistical analysis of the primary and secondary endpoints will be performed on an intention-to-

treat basis, which will provide an unbiased assessment of the efficacy of the intervention.

13.2. Other measures taken to minimise / avoid bias

The statistical analysis will include checks on potential bias in the extent of surgery, as surgeons will

be aware of randomised treatment before beginning the operation. Specifically, the specimen weight

and total specimen size will be compared between the treatment arms.

TARGIT B Protocol IRAS No: 77045 Version 6.0, Dated 10/09/2018 14. Data

14.1. Data to be collected

Data will be collected on case record forms (CRFs), including baseline, follow-up and safety data.

All CRFs are mandatory, except those that are required on an "as and when" basis (for example, the

local recurrence form).

Patient Follow-up and recording of events, notification of recurrence, adverse events and

death

Patients should be followed according to local guidelines and these should be noted on the Policy

Statement prior to entry into the trial. However, case report forms will be required for each patient

at 6 monthly intervals for the first three years and annually thereafter until at least 10 years.

Wherever possible each patient should be seen within a six week window of the anniversary of the

date of randomisation (e.g. at 12 months \pm 6 weeks). At each visit the patient should be offered a

physical examination and asked whether she has experienced any adverse events.

We recommend that mammography occurs annually. Any other examination is at the discretion of

the local clinician.

Recording of recurrence/new malignancies

Recurrence includes any new occurrence of breast cancer apart from new disease in the opposite

breast in the absence of previous recurrence (which is classified as a contralateral breast cancer).

Local recurrence, for the purposes of this protocol, is defined as recurrence in the ipsilateral breast.

Loco-regional recurrence is defined as recurrence either in the ipsilateral breast and/or in the axilla.

Ipsilateral supraclavicular and intramammary node recurrence are not classified as local recurrence

since the prognosis of patients with recurrence at these sites is more similar to distant than loco-

regional disease.

Confirmation of ipsilateral recurrence must be by histology or unequivocal cytology. Clinical

examination and imaging are not sufficient. Careful recording of the site of the recurrence is required

to determine whether it is at the site of the original tumour and/or within the treatment field.

Recurrence at any other site must be confirmed by appropriate imaging and/or biopsy. Details of

both first ipsilateral local, loco-regional (breast and axilla) and first distant recurrence are required as

well as the status of the patient with regard to active disease when treatment for local disease has been

completed.

TARGIT B Protocol IRAS No: 77045 Version 6.0, Dated 10/09/2018 Development of new malignancy (including the contralateral breast) must be reported on the case

report forms once a diagnosis has been confirmed. Cause of death must be recorded accurately.

Guidelines for the Management of Recurrence

The management of recurrent disease will be left to the discretion of the participating

institution/investigator. If appropriate, patients having had TARGIT alone are able to have

conventional irradiation as part of the management of a recurrence. It may also be possible for patients

who have received external beam treatment to have TARGIT after surgical excision of the recurrence,

particularly if they wish to avoid mastectomy.

14.2. Adverse Events

This section describes the minimum reporting procedures for the trial, based on current UK and

European Union legislation. Local and national policies may require additional reporting of safety

data, including adverse events.

The Trial Steering Committee and the DMC will review data on adverse events and complications.

If a local or national policy requires a summary of this review (e.g. for an annual report), please

contact the TARGIT Trial Operations Office.

Acute and late radiation morbidity must be graded according to established criteria such as LENT-

SOMA and RTOG; the criterion 'pain due to radiation' will be graded according to the Common

Toxicity Criteria ²⁴. These are the only expected adverse events and would cover most events, any

other adverse events must be recorded on the 'Adverse Event' log (TB29.0). Adverse events may be

recorded at any time following the surgery and a new form should be completed for each episode.

Any complications following surgery (± TARGIT) must also be reported on the complication forms.

Serious Adverse Events

Serious adverse events (SAEs) are defined as any event that is fatal; life threatening; causes or

prolongs hospitalisation; causes disability or incapacity or requires medical intervention to prevent

permanent impairment or damage, any grade 4 toxicity.

Reporting Requirements

Immediate reporting of any SAEs must be made directly to the TARGIT Trial Operations Office as

soon as possible and at least within 5 working days of the investigator becoming aware of the

occurrence of the event. The TARGIT Trials Office will email all SAE forms to research-

TARGIT B Protocol IRAS No: 77045

Version 6.0, Dated 10/09/2018

Page 31 of 46

[contact]. SAEs must be reported whether or not considered related to the treatment under

investigation. An early report can be followed up by a more detailed report.

SAEs directly caused by chemotherapy (e.g. febrile neutropenia) do not need to be reported to the

trial centre.

All serious adverse events that occur during the period of observation (see next section) must be

documented on the 'Serious Adverse Event Form'. It is also the investigators' responsibility to report

them to the local institutional ethics committee as required by local regulations.

• For all serious adverse events, the following must be assessed and recorded on the SAE

reporting form: intensity/severity; relationship to treatment; action taken; outcome to date.

• Adverse events must also be recorded in the subject's medical records.

The clinical course of the serious adverse event should be managed according to accepted standards

of medical practice until a satisfactory explanation is found or the investigator considers it medically

justified to terminate follow-up of this event. Should the adverse event result in death, a full

pathologist's report should be supplied, if possible.

Period of Observation

For the purpose of this trial the period of serious adverse event (SAE) observation extends from the

time of registration onto the trial until 90 days after the completion of randomised treatment. Trial

follow-up should continue according to schedule once the SAE is resolved.

SSARs (Suspected Serious Adverse Reactions)

Suspected Serious Adverse Reactions are adverse reactions (or events) that are thought to be related

to the research procedure. For the purpose of this trial the following is a list of potential SSARs:

Fibrosis

Delayed wound healing

Wound infection

Wound breakdown

Haematoma in breast or axilla

Seroma

Dermatitis associated with radiation

Telangiectasia

Pain in irradiated field

Oedema

TARGIT B Protocol IRAS No: 77045 Version 6.0, Dated 10/09/2018

Page 32 of 46

SSARs should be reported as described in 14.2

SUSARs (Suspected Unexpected Serious Adverse Reactions)

Suspected Unexpected Serious Adverse Reactions are adverse reactions (or events) that are thought

to be related to the research procedure but do not appear on the list of SSARs. SUSARs should be

reported within 24 hours as described in 14.2.

Deaths

All deaths, with date and cause, must be reported as soon as possible to the TARGIT Trial Operations

Office on the appropriate CRF. Deaths which also meet the SAE criteria should additionally be

reported as described in 14.2.

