access to the Intrabeam® (Carl Zeiss) are eligible to enter patients into the trial.

Eligible patients are those with a higher risk of local recurrence after breast conserving surgery. After

giving consent patients are randomised to either TARGIT Boost or EBRT Boost. All patients will

receive whole breast EBRT. They may receive any other adjuvant treatments as deemed necessary.

The protocol recommends that patients be followed at six monthly intervals for three years and then

annually.

The primary endpoint is ipsilateral breast recurrence rate. Secondary endpoints are relapse-free

survival, site of recurrence, overall survival (breast-cancer specific and non-breast cancer deaths)

quality of life and cost-effectiveness. Cosmetic outcome, cardiopulmonary toxicity, patient

satisfaction and patient preference will be discussed in separate subprotocols.

TARGIT B Protocol IRAS No: 77045 Version 6.0, Dated 10/09/2018

Page 8 of 46

6. Background

Patients receiving breast conservation surgery benefit from radiotherapy to the whole breast ¹ as well

as a tumour bed boost. Although the absolute benefit is higher in absolute terms in younger women,

they still have a high recurrence rate (e.g., 8.7% and 13.5% for those <50 years and <40 years

respectively in the EORTC study ²). The reasons for this could be an inherent resistance to

radiotherapy but the following issues need attention:

Geographical miss: Targeting the boost dose to the tumour bed can be difficult; the use of ultrasound

or clips may help but it is not universal and with increasing use of oncoplastic surgery, the

configuration of the tumour bed can become completely distorted. Thus in many cases the potential

benefit of the boost may be reduced ³.

Temporal miss: Our translational work found that surgical wound fluid stimulates proliferation,

migration and invasion. This stimulation of cancer cells by the normal response to wounding may

contribute to local recurrence, especially in younger women who may evolutionarily mount a stronger

response to wound healing. Interestingly, this effect is abrogated by targeted intraoperative

radiotherapy (TARGIT) which utilises a window of opportunity that has always been missed by

traditional radiotherapy, through the novel effect of radiotherapy on tumour microenvironment ⁴.

Addition of this effect to the tumouricidal effect of radiotherapy may significantly improve outcomes.

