Quality of life: The primary PRO endpoint for QOL will be the FACT-B+4 trial outcome index (TOI)

score. The TOI score (0-180) is a sum of the scores of the 27 items included in the physical well-

being, functional well-being and breast cancer subscales of the FACT-B+4. A change of at least 5

points in TOI is considered to be clinically relevant or a minimally important difference (Eton et al.

2004). Secondary endpoints will be: 1) the five item arm functioning subscale score (0-20) 2) The 40

item FACT B+4 score (0-160), which reflects global quality of life including social and emotional

well-being.

Health economics: resource use, HR QOL and cost-effectiveness.

Sub-protocols

The following sub-protocols are planned for the TARGIT B Trial. Each will have their own protocol,

patient information leaflet and consent form; they have been included for completeness.

TARGIT B Protocol IRAS No: 77045 Version 6.0, Dated 10/09/2018

Page 16 of 46

A concurrent sub-protocol will assess cosmesis in a sub-set of patients. Patient's own assessment of

cosmesis will be used along with objective assessment from a frontal digital photograph. The

assessments will be made annually and assessed, blind to treatment, using specialist, validated

software (BCCT.core 2.0, INESC Porto, Portugal) which produces a composite score (Excellent,

Good, Fair, Poor) based on symmetry, colour and scar. We have used this tool already within the

TARGIT-A trial and recently presented some results ¹⁷

A patient preference subprotocol will be an interview-based determination asking patients whether

they would choose EBRT or TARGIT given hypothetical recurrence risks. This approach has been

used in the TARGIT A Trial.

A cardio-pulmonary subprotocol will assess the degree of radiotherapy-induced heart and lung

damage. The less penetrating X-rays from Intrabeam are expected to cause less damage, but this

should be formally tested.

These sub-protocols will be subject to their own sponsorship and regulatory reviews.

Assessment and follow up

The schedule for assessment and follow-up will be as follows:

Baseline (soon after surgery), pre-EBRT (around 6 months), 12, 18, 24, 30, 36, 48, 60, 72, 84, 96,

108, 120 months.

Assessment of efficacy/effectiveness:

Follow-up will be balanced between the two arms and be at least every 6 months for the first 3 years,

then annually to 10 years. Each follow up will include clinical history and examination and

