mammograms as per local guidelines, but at least annually for the first 5 years and/or then until the

patient is eligible for national screening programme.

Assessment of safety:

Local toxicity and morbidity will be recorded as adverse events related to the primary treatment of

breast cancer. The expected toxicities of acute skin reaction, wound infection, wound breakdown,

late skin reactions (i.e. after 90 days) and pain due to radiation will be graded according to RTOG

and LENT SOMA criteria. Any other toxicity will be recorded and graded according to standard

clinical criteria.

TARGIT B Protocol IRAS No: 77045 Version 6.0, Dated 10/09/2018

0, Dated 10/09/2018 Page 17 of 46

Data on safety will be gathered from the following forms: Serious Adverse Event, Protocol

Violation/Deviation, and Complication Form. These forms will collect treatment related adverse

events, including postoperative complications such as haematoma, seroma, wound infection, skin

breakdown, and delayed wound healing.

Upon receipt of a completed form the TARGIT Trials Office will ascertain that the event meets the

definition of a SAE, and if required, actively ensure full completion of other related forms such as

the complications form. It is the responsibility of TARGIT Trials Office personnel to provide

summary information to the TSC or DMC. Any local requirements of reporting SAEs to IRB or local

EC are the responsibilities of the investigator.

Functional Assessment of Cancer Therapy-Breast +4

Quality of life will be assessed using the Functional Assessment of Cancer Therapy-Breast +4

questionnaire (FACT-B+4). The FACT-B is a validated instrument comprised of several subscales:-

physical well-being (7 items), social well-being (7 items), emotional well-being (6 items), functional

well-being (7 items), and concerns specific to patients with breast cancer (13 items). It provides a

comprehensive measure of overall health related quality of life and has been used in many large

clinical trials of breast cancer treatment. However the FACT-B has only a single item about arm

morbidity so 4 additional items were added creating a validated arm morbidity sub-scale to use with

the FACT B evaluating swelling/tenderness, numbness, painful movement, range of movement and

stiffness, (FACT-B+4).

Patients indicate, using a five-point scale ranging from 0 (not at all), 1 (a little bit), 2 (somewhat), 3

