11.2. Use within the trial

Patients with positive margins: If final pathology shows involved or close margins (evidence of

invasive or in situ tumour at, or within 1mm, of an excision margin or 'ink-on-margin' as per local

practice and multidisciplinary team discussion) re-excision is strongly recommended. In some cases,

this may necessitate a mastectomy. Decision about re-excision or mastectomy should not be

influenced by whether the patient had received TARGIT-Boost or not. For patients who have already

received TARGIT, such re-excision to clear margins should be followed by external beam

radiotherapy excluding the boost. Intraoperative radiotherapy or EBRT boost of the re-excised tumour

bed which had previously received TARGIT should not be done because we have had no experience

regarding its safety.

The procedure for delivering the TARGIT is described below, including the administration of a

prophylactic antibiotic just after the induction of anaesthesia. In this group of patients, special care

should be taken to ensure the wound closure is meticulous, air- and water-tight and sutures are not

removed for at least 2 weeks. If an absorbable suture is used it should be at least 3-0 in thickness,

should not be absorbable within 2 weeks and Steristrips should be used and left in situ for 2 weeks.

Also, in this group the antibiotic cover should be for 5 days.

Pathological Examination: Data from pathological examinations should be recorded on the

appropriate data collection forms and all reporting of pathological findings are to be in accordance

with the TNM Classification.

Radiotherapy

TARGeted Intra-operative radioTherapy (TARGIT): The technique of the operation and the delivery

of radiotherapy have been described in a video available from the TARGIT Trial Operations Office

and at http://www.youtube.com/watch?v=GVlHGpvRf8A. We have established a standard training

protocol before any centre is allowed to recruit into the trial. We shall ensure that the doses are

standardized between all centres.

Preparation of the Intrabeam: TARGIT will either be delivered in the operating theatre immediately

after the removal of the tumour or as a subsequent procedure, a short time later. The procedure has

been described in detail ^{8 9 18}. The device and the arm of the stand are wrapped in a sterile clear plastic

cover. The individual applicators are sterilised prior to the theatre session. The size of the sphere is

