only be delivered to those patients who are randomised to the EBRT boost arm and they should

preferably receive this in the form of 16Gy in 8 fractions over 1.5 weeks with electrons of appropriate

energy². We believe that external beam radiotherapy planning should be image guided using tumour

bed localisation clips as described in the IMPORT trials ²¹. Although a centre would not be excluded

from the study if this is not being practised (as stratification of randomisation will balance the two

arms), we shall strongly recommend its use. VBH or a similar technique can be used to reduce

exposure of internal organs to unnecessary radiation.

Adjuvant Systemic Therapy: Trial patients may be recommended appropriate adjuvant systemic

therapy according to local practice or trial protocols. The sequencing of these other therapies is not

governed by this protocol, but the policy for such treatment-sequencing should be declared in the

Policy Statement (e.g. it should be declared whether the EBRT will be delivered before or after

chemotherapy).

Patient Compliance: Compliance is likely to be high because the treatment is given during

surgery. Some patients will refuse the allocated therapy between randomisation and surgery, but

[figure not shown]
based on our experience with more than 3000 patients from the TARGIT A Trial we think the number

will be minimal.

TARGIT B Protocol IRAS No: 77045

The Technology

The recent development of a new method has made possible the delivery of radiation directly to the tissues at the site of the primary tumour. The Intrabeam® (originally developed by the Photoelectron Corporation in Massachusetts, USA, but now manufactured by Carl Zeiss, Germany) is a simple but ingenious device, in essence a miniature electron beam-driven X-ray source which provides a point source of low energy X-rays (50kV maximum) at the tip of a 3.2mm diameter tube. The radiation source can be inserted into the area of interest immediately after excision of the tumour (Figure 1) and switched on for 20-35 minutes to provide intra-operative radiotherapy accurately targeted to the tissues that are at highest risk of local recurrence. The physics, dosimetry and early clinical applications of this soft x-ray device have been well studied and the probe has already been used for treatment of human malignant brain tumours. ^{8 9 22}

Figures 1 (a) and (b)

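### SAE observation ends 90 days after an undefined randomised treatment; read literally, the EBRT-boost arm is observed 1.8 to 3.5 times as long after surgery, which skews crude SAE counts towards TARGIT

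*Protocol*

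**What the plan says.** Section 14.2 (Period of Observation) runs SAE observation from the "time of registration onto the trial until 90 days after the completion of randomised treatment". The end of the window therefore depends on when treatment finishes, not on a date common to both arms. The protocol does not define randomised treatment for this purpose.

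The Summary (section 5) identifies what is randomised. Across a line break it reads "giving consent patients are randomised to either TARGIT Boost or EBRT Boost. All patients will" and "receive whole breast EBRT. They may receive any other adjuvant treatments as deemed necessary". Section 7 likewise has the single intra-operative dose substitute for the usual boost, with whole-breast EBRT as background.

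On timing:
- Section 11.2 has TARGIT delivered in theatre straight after tumour removal, or in a further procedure soon afterwards.
- Section 11.2 says control patients should "preferably receive this in the form of 16Gy in 8 fractions over 1.5 weeks". It gives 15 or 25 fractions as examples of acceptable whole-breast courses.
- The visit list in section 8 opens "Baseline (soon after surgery), pre-EBRT (around 6 months", then continues at 12 months and beyond.
- Section 11.2 leaves the sequencing of EBRT and chemotherapy to each centre's declared policy.

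On scope, section 14.2 requires SAE reports regardless of relatedness and exempts SAEs directly caused by chemotherapy. Ordinary adverse events may be recorded at any time after surgery, and deaths are reported without a time limit. Section 8 also grades, among the expected toxicities, "late skin reactions (i.e. after 90 days) and pain due to radiation".

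**The concern.** If the boost is the randomised treatment, the 90-day clock starts at very different times in the two arms. For a TARGIT patient it starts at surgery or shortly after. For a control patient it starts only when the external-beam boost is finished. Because unrelated SAEs count too, the longer window collects more events.

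Two things are at stake. First, a crude comparison of SAE counts or proportions would favour TARGIT through observation time alone. Second, where EBRT starts late, a TARGIT patient's window has closed before her whole-breast EBRT begins. Serious reactions to TARGIT followed by whole-breast EBRT, which is the experimental policy, then fall outside SAE reporting. An analysis plan cannot repair this later, because the forms would never have been collected.

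**Working it through.** The protocol states no figure for this window, so there is nothing to reproduce.

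**Inputs**
- Tail after completion: 90 days (section 14.2).
- TARGIT boost complete: day 0, taken as surgery (section 11.2; slightly later if given as a further procedure).
- EBRT start: about 6 months, taken as 183 days (visit label, section 8). Starts at 6 weeks (42 days) and 12 weeks (84 days) are assumptions, used to show a range.
- Whole-breast course: 15 or 25 fractions (section 11.2), taken as 21 or 35 days on an assumed five fractions a week.
- EBRT boost: 1.5 weeks = 10.5 days (section 11.2), assumed to follow whole-breast EBRT.
- Patients: 898 per arm (section 15.1).

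**Window lengths after surgery**

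TARGIT: 0 + 90 = 90 days. Control: EBRT start + whole-breast course + 10.5 + 90.

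| EBRT start | 15 fractions | 25 fractions | Ratio to 90 days |
|---|---|---|---|
| 42 days (assumed) | 163.5 | 177.5 | 1.82 to 1.97 |
| 84 days (assumed) | 205.5 | 219.5 | 2.28 to 2.44 |
| 183 days (visit label) | 304.5 | 318.5 | 3.38 to 3.54 |

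The time from registration to surgery adds the same amount to both arms and lowers the ratios slightly. At 183 days, whole-breast EBRT lies wholly outside the TARGIT window. At 84 days it starts inside and ends outside. At 42 days it ends inside (day 63 or 77), but most of the 90 days after it are lost.

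**Effect on counts if SAEs arise at a constant, equal hazard**

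Formula: p = 1 − exp(−rate × window/365.25); expected patients = 898 × p. The rates are assumptions. With 15 fractions, at 0.10 per person-year and a 183-day start: control p = 1 − exp(−0.10 × 304.5/365.25) = 0.0800, or 72 patients; TARGIT p = 1 − exp(−0.10 × 90/365.25) = 0.0243, or 22.

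| EBRT start | Control vs TARGIT, 0.10/year | Chance of p < 0.05 for TARGIT | Control vs TARGIT, 0.05/year | Chance of p < 0.05 for TARGIT |
|---|---|---|---|---|
| 42 days | 39 vs 22 | 0.62 | 20 vs 11 | 0.36 |
| 84 days | 49 vs 22 | 0.91 | 25 vs 11 | 0.65 |
| 183 days | 72 vs 22 | 1.00 | 37 vs 11 | 0.97 |

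The chances are the power of a two-sided 5% comparison of two proportions with 898 per arm. They illustrate the artefact; section 15.2 plans no such test.

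**Effect if SAEs cluster around surgery**

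Assume 5% of patients in both arms have a surgical SAE, and whole-breast EBRT adds 1% to 2% that only the control window captures. Control: 898 × 0.06 = 54 to 898 × 0.07 = 63. TARGIT: 898 × 0.05 = 45. TARGIT then shows 45/54 = 83% to 45/63 = 71% of the control count, and the chance of a nominally significant result is 0.15 to 0.43. The direction is the same and the size much smaller.

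**Why dividing by observation time does not help**

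In the 5% plus 1% case with the 304.5-day window, control is 0.06/(304.5/365.25) = 7.2 per 100 person-years and TARGIT is 0.05/(90/365.25) = 20.3. The bias reverses instead of disappearing.

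**The case against.** The strongest reply is that the term is undefined, and other text allows a wider meaning. Section 6 uses the TARGIT-Boost label for an intra-operative boost followed by whole-breast radiotherapy. Section 8 describes two approaches to adjuvant radiotherapy. Section 16.1 checks compliance with randomised treatment through both the intra-operative and the external-beam forms, although the latter may simply capture the EBRT boost. If the term means the whole allocated strategy, both windows cover whole-breast EBRT and differ only by the boost course: on the 183-day start with 15 fractions, 294 vs 304.5 days. This stands as a real ambiguity. Sections 5 and 7 favour the narrower reading, though, and an undefined term lets sites apply either.

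The 6-month figure is a visit label, not a rule on when EBRT starts, and sequencing is local. So the loss of all of whole-breast EBRT from the TARGIT window cannot be assumed for every patient. That also stands. The unequal length remains at the earlier assumed starts.

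Other safety data are not cut off at 90 days: ordinary adverse events, complication forms, graded acute and late radiation morbidity, and deaths. The trial and data monitoring committees review adverse events and complications generally. This limits the problem to SAE-form data but does not remove it, because those other forms do not carry the SAE route's 5-working-day reporting.

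Finally, the suspected serious reactions listed include fibrosis and telangiectasia, which may appear late. A 90-day tail truncates such reactions in both arms, so this is a question of completeness and not a source of between-arm bias.

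**Conclusion.** As written, and on the reading that sections 5 and 7 support, the SAE window is unequal by design: 90 days after surgery for TARGIT against about 164 to 319 days for control. Crude SAE counts or proportions are then biased towards TARGIT. This rests on the boost being the randomised treatment, on the boost following whole-breast EBRT, on five fractions a week and on the EBRT start times shown.

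A reader might infer from the window ratios that TARGIT would show only about 30% to 50% of the control arm's SAEs. The documents do not support that. It needs a constant hazard, whereas many of the listed reactions (wound problems, haematoma, seroma) are largely perioperative and SAEs directly caused by chemotherapy are exempt. Even with a constant hazard, the 6-week start gives 22/39 = 56%. A reader might also infer that the whole harm comparison is biased; only the SAE-form data are. The direction is clear for crude measures, but the size depends on SAE rates and timings that the protocol does not give.

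**What to change.** Replace the sentence in section 14.2 with one SAE collection window for both arms that does not depend on the allocated boost and covers whole-breast EBRT in both. A fixed period from randomisation would do, provided it is long enough to include 90 days after the last protocol radiotherapy. On the longest case above, that means at least 318.5 days after surgery plus the time from randomisation to surgery, and more where a centre's declared sequencing puts EBRT later. Ending the window 90 days after the last fraction is not enough by itself, because the control window would still be longer by the boost course.

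Compare arms on the proportion with an SAE, or on time to first SAE, over that identical period from randomisation. Do not use rates per unit of unequal observation time.

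State separately whether serious reactions on the suspected-reaction list remain reportable after the window closes. This applies equally to both arms.

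The cost is a short protocol amendment and some additional SAE forms, mainly in the TARGIT arm. The existing exemption for chemotherapy-caused SAEs limits that burden.
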